9.3.7 Change from Baseline in FiO_2 at each Timepoint After Treatment

Actual values and change from baseline in FiO_2 at 6 and 12 hours following each treatment medication administration in the poractant alfa group and then each 24 hours till the subject is discharged from the ICU and similar timepoints in the control group (defined as 6 and 12 hours after randomization for Day 1, 30 and 36 hours after randomization for Day 2 and 54 and 60 hours post randomization for Day 3 and then each 24 hours till the subject is discharged from the ICU) will be described.

9.3.8 Length of ICU Stay at Day 28

The length of ICU stay (in days) will be calculated as: MIN (date of ICU discharge, date of Day 28) – date of ICU entrance + 1.

In case of readmission in ICU, the duration of the primary one and the readmission will be added. Lengths of ICU stay will be presented in total.

Subjects who die or are mechanically ventilated longer than this period will be assigned with a 28 days length value.

Those subjects will be identified using:

- On Study Completion form, death date is filled and $< \text{MIN} (\text{date of ICU discharge, date of Day 28})$
- On Ventilatory Support form the subtype Invasive- Mechanical ventilation is ticked and $(\text{End Date} - \text{Start Date}) + 1 > 28 \text{ Days}$ or if Ongoing is ticked (i.e. subject still under mechanical ventilation at the end of the Study).

In case of multiple sessions of Invasive- Mechanical ventilator support without any discharge in between the MIN start date and the MAX end date will be taken into account.

It will be presented using descriptive statistics by treatment group.

A graph displaying the mean and SD for each timepoint (until the subject is discharged from ICU) will be also provided for each treatment group.

9.3.9 Percentage of Subjects Alive and Out of ICU at Day 28

The subject will be defined alive and out of ICU at Day 28 if:

- On Patient Status form at "D28 – FU" visit, the subject is still alive

AND

- Date of ICU discharge Visit < Date of “Day 28 – FU” visit

The percentage will be summarized.

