4.1.2.2 Others Secondary Efficacy Variables

- Number of days alive and ventilator-free **at Day 28**
- Mortality **at Day 21 and Day 28**
- Number of days alive and free from invasive ventilation **at Day 21 and Day 28**

- Number of days alive and free from non-invasive ventilation (NIV) at **Day 21 and Day 28**
- Percentage of subjects with improvement in severity status defined as a decrease in the severity score at **Day 28 or Discharge**, whichever comes first. Severity score will be defined as Mild, Moderate, Severe or Death based on PaO₂/FiO₂ ratio and subject status at Day 28 and numerically rated from 1-4 respectively:

Severity	Variable	Criteria
Mild -1	PaO ₂ /FiO ₂ Ratio	200 mmHg < PaO ₂ /FIO ₂ ≤ 300 mmHg
Moderate - 2	PaO ₂ /FiO ₂ Ratio	100 mmHg < PaO ₂ /FIO ₂ ≤ 200 mmHg
Severe - 3	PaO ₂ /FiO ₂	Ratio PaO ₂ /FIO ₂ ≤ 100 mmHg
Death - 4	Patient Status	Yes/No

- Change from baseline in PaO₂/FiO₂ ratio at **6 and 12 hours following administration of each dose** in the treated group and at the similar timepoints in the control group (6, 12, 30, 36, 54 and 60 hours after randomisation)
- Change from baseline in PaO₂/FiO₂ ratio at additional timepoints (i.e. every 24 hours after treatment/randomisation until the subject is discharged from the ICU)
- Percentage of subjects alive and with PaO₂/FiO₂ improvement of >20% at **6 and 12 hours following administration of each dose** in the treated group and at similar timepoints in the control group (6, 12, 30, 36, 54 and 60 hours after randomisation)
- Percentage of subjects alive and with PaO₂/FiO₂ improvement of >20% at the additional timepoints (i.e. every 24 hours after treatment/randomisation till the subject is discharged from the ICU)
- Change from baseline in FiO₂ at **6 and 12 hours following administration of each dose** in the treated group and at similar timepoints in the control group (6, 12, 30, 36, 54 and 60 hours after randomisation)
- Change from baseline in FiO₂ at additional timepoints (i.e. every 24 hours after treatment/randomisation until the subject is discharged from the ICU)
- Length of ICU stay (days) **at Day 28**. Subjects who die or are mechanically ventilated longer than this period are assigned with 28 days
- Percentage of subjects alive and out of ICU **at Day 28**
- Delta SOFA Score and sub-score component measured on **Day 3 and Day 28 or Discharge** whichever comes first

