7.9.3 Study Day

If not otherwise specified, all assessment days will be related to date of randomization.

The randomization date is referred to as Day 1.

- If the date of the assessment is on or after the randomisation, then
Study Day = (date of assessment – randomisation date) + 1.
- If the date of the assessment is prior to the randomisation, then
Study Day = (date of assessment – randomisation date).

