8.2.2 SAS COVID-19 ARDS History

Days between screening positive SARS-COV-19 rt-PCR test and start of intubation, days between ICU admission date and start of intubation, and SARS COVID-19 ARDS medication categories recorded at Screening Visit will be presented by treatment group and overall for Safety Set.

In addition, SAS COVID-19 ARDS history data will be presented in an individual listing.

Notes:

- Days between screening positive SARS-COV-19 rt-PCR test and start of intubation = Start date of intubation – Date of screening positive SARS-COV-19 rt-PCR test + 1.
- For subject with intubation done after ICU admission: Days between ICU admission date and start of intubation = Start date of intubation – Date of ICU admission + 1.
- For subject with intubation done before ICU admission (transfer from another hospital): Days between ICU admission date and start of intubation = Start date of intubation – Date of ICU admission.

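### SAP 9.3.8 leaves deaths after ICU discharge with short ICU stays and lets some survivors exceed the 28 days assigned to a death

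*SAP*

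**What the plan says.** The endpoint definition is unconditional. SAP 4.1.2.2 has "Subjects who die or are mechanically ventilated longer than this period are assigned with 28 days", and protocol sections 8 and 12.3.5 say the same. SAP 9.3.8 repeats it, and the second footnote planned for Table 14.2.11 would print it.

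SAP 9.3.8 then gives the derivation:

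- **Stay.** "The length of ICU stay (in days) will be calculated as: MIN (date of ICU discharge, date of Day 28") minus "date of ICU entrance + 1". Readmissions are added. No upper limit is stated.
- **Deaths.** A subject gets 28 for death if a death date is present and is strictly earlier than the minimum of the ICU discharge date and the Day 28 date.
- **Ventilation.** The test begins "On Ventilatory Support form the subtype Invasive- Mechanical ventilation is ticked and" and requires either more than 28 days from ventilation start to ventilation end, counted inclusively, or the Ongoing box ticked.

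Day 28 is counted from randomisation. SAP 7.9.3 says "The randomization date is referred to as Day 1". ICU entrance is not tied to randomisation. SAP 8.2.2 has one formula for a case it words as "For subject with intubation done after ICU admission" and another for intubation before ICU admission, and neither sets a maximum interval.

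**The concern.** Assigning 28 days to deaths is meant to stop an early death from looking like a quick ICU discharge. The identification rule defeats this for patients who leave ICU alive and die later. SAP section 2 says that transfers from ICU to other departments are likely and that follow-up continues after them, so such deaths can occur and be recorded. Protocol section 1.1 expects mortality of 30–70% in COVID-19 patients treated on ICU, so the handling of death matters for this endpoint.

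The second problem is the ordering of outcomes. Deaths are fixed at 28, while the stay of a survivor starts at ICU entrance and can run past 28. The excess is made of days before randomisation, which treatment cannot affect.

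**Working it through.** The plan gives no figure for this endpoint to reproduce. Its 84% power concerns the primary endpoint and does not bear on this point.

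**Setting.** Dates are offsets from randomisation: Day d is offset d − 1, so Day 28 is offset 27. ICU entry k days before randomisation is offset −k. The documents do not give k, so its values below are assumptions. A missing ICU discharge date is ignored in the minimum, which is also an assumption.

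Stay = MIN(discharge, 27) + k + 1.

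**1. Death after ICU discharge.** Assume k = 2, discharge on Day 8 (offset 7) and death on Day 15 (offset 14).

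- Death test: MIN(7, 27) = 7, and 14 < 7 is false, so the death is not identified.
- Ventilation test: not met if the patient left ICU off invasive ventilation.
- Stay: 7 + 2 + 1 = 10. The definition requires 28, a difference of 18 days.

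The result does not depend on the strict inequality. Any death after the ICU discharge date fails the test, because ICU discharge sits inside the minimum.

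One such patient lowers the mean of a control arm of the planned size by 18/28 = 0.64 day, and that of a poractant alfa arm of the planned size by 18/42 = 0.43 day. SAP section 12 says recruitment stopped short of 70. In an arm assumed to hold 10 patients the shift would be 18/10 = 1.8 days.

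**2. Survivor in ICU at Day 28, off invasive ventilation, ventilated no more than 28 days.** Stay = 27 + k + 1 = 28 + k.

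| k (assumed) | Survivor | Death that meets the test |
|---|---|---|
| 0 | 28 | 28 |
| 1 | 29 | 28 |
| 2 | 30 | 28 |
| 5 | 33 | 28 |
| 10 | 38 | 28 |

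A survivor discharged on Day D scores D + k. With k = 10 and D = 20 the value is 30, again above that of a death.

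**3. Death dated the same day as ICU discharge.** Assume k = 1 and death in ICU on Day 6 (offset 5).

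- Discharge entered as the death date, ventilation not marked Ongoing: 5 < 5 is false, and the stay is 5 + 1 + 1 = 7.
- Discharge date left blank: MIN = 27, 5 < 27 is true, and the value is 28.
- Ventilation marked Ongoing: the value is 28 through the ventilation test.

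**4. Ventilation clock.** Protocol inclusion criterion 6 allows intubation up to 48 hours before the first dose. Assume ICU entry and intubation 2 days before randomisation, with the patient alive in ICU at Day 28.

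- Extubated on Day 26: 25 + 2 + 1 = 28 ventilated days, not above 28, so the stay is 27 + 2 + 1 = 30.
- Extubated on Day 27: 26 + 2 + 1 = 29 ventilated days, above 28, so the value is 28.

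The patient ventilated one day longer gets the better value.

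**The case against.** The strongest reply is that little depends on this variable. It is one of many secondary endpoints, and SAP section 12 drops its formal comparison. SAP 7.8 reports medians beside means. Mortality at Days 21 and 28 and the percentage alive and out of ICU are summarised separately, and Listing 16.2.6.2-b shows mortality with each ICU stay. All of that stands and limits the importance of the point. It does not make the Table 14.2.11 footnote true, and section 12 declares no narrower rule for deaths.

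A second reply is that the endpoint names no start for the stay, so counting from ICU entrance is a legitimate choice. That is partly right. The defect is an uncapped stay set beside a fixed 28. Starting at randomisation is one way to remove it.

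A reader might also infer more than the documents support:

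- **That deaths in ICU are generally scored short.** This needs discharge entered as the death date and ventilation not marked Ongoing. The documents do not state that convention. Protocol 7.1.4 describes ICU discharge as a visit with assessments, which points towards a living patient but does not settle the question.
- **That the strict inequality is the cause.** It explains only ties. Allowing equality would not rescue a ward death.
- **That the ventilation clock is an equal defect.** A patient extubated in ICU on Day 27 has at least 27 ICU days from randomisation, so the 28 assigned is at most one day from the corrected value.
- **That the SAP expects ICU entry before intubation.** SAP 8.2.2 provides for both orders.
- **That the arm means would reverse.** The examples are single patients, and nothing in the documents shows a reversal.

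**Conclusion.** The point holds in a limited form. SAP 9.3.8 contradicts the endpoint definition for every subject who dies after ICU discharge and by Day 28, unless the ventilation test happens to apply. In the worked case the error is 18 days, under assumed dates.

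Separately, the uncapped stay scores some survivors 28+k, worse than a death whenever k is 1 or more. With k = 0 and a single stay the two tie at 28. The size rests on k, which the documents do not give.

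The same-day death is conditional on how the eCRF is completed, and the ventilation clock is a minor inconsistency. The consequence is distortion in the reported summaries of one secondary endpoint. No planned test changes, and the number of patients affected cannot be computed from the documents.

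**What to change.** In SAP 9.3.8:

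1. Assign 28 to every subject with a death date on or before Day 28, whatever the ICU discharge date.
2. Assign 28 to every subject still on mechanical ventilation on Day 28. Either use the SAP 4.1.1 definition (invasive and non-invasive) or state that only invasive ventilation counts, as the present test does.
3. For all others, count ICU days from randomisation (Day 1) to Day 28, summing stays and counting each calendar date once, so that no value exceeds 28.
4. Report ICU days before randomisation as a baseline item.
5. Align the first footnote of Table 14.2.11, which repeats the present formula.

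Death will then be tied for the worst value, because a survivor in ICU through Day 28 also scores 28. The text should say so.

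The cost is SAP wording, one reprogrammed derived variable and a small baseline summary. The dates are already collected. If the SAP is not reopened, the change can be explained in the clinical study report, as SAP section 1 provides for deviations.

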- Percentage of patients alive and with PaO₂/FiO₂ improvement of >20% at the additional timepoints (i.e. every 24 hours after treatment/randomisation till the patient is discharged from the ICU)
- Change from baseline in FiO₂ at **6 and 12 hours following administration of each dose** in the treated group and at similar timepoints in the control group (6, 12, 30, 36, 54 and 60 hours after randomisation)
- Change from baseline in FiO₂ at additional timepoints (i.e. every 24 hours after treatment/randomisation until the patient is discharged from the ICU)
- Length of ICU stay (days) **at Day 28**. Patients who die or are mechanically ventilated longer than this period are assigned with 28 days
- Percentage of patients alive and out of ICU **at Day 28**
- Delta SOFA Score and sub-score component measured on **Day 3 and Day 28 or Discharge** whichever comes first
- Percentage of patients alive and organ failure free (SOFA score=0) **at Day 28 or Discharge** whichever comes first
- Change from baseline in ventilatory parameters [tidal volume (TV), respiratory rate (RR), dynamic compliance (C_{dyn}), static compliance (C_{stat}), positive end-expiratory pressure (PEEP), peak inspiratory pressure (PIP), plateau pressure (P_{plat})] measured at 6-12-24h after each poractant alfa administration up to 72 hours and at similar timepoints in the control group (6, 12, 24, 30, 36, 48, 54, 60 and 72 hours after randomisation) and then every 24 hours till the patient is discharged from the ICU
- Change from baseline in blood gas analysis acid-base balance parameters (i.e. pH, pCO₂, pO₂, HCO₃, lactate) measured at 6-12-24h after each poractant alfa administration up to 72 hours and at similar timepoints in the control group (6, 12, 24, 30, 36, 48, 54, 60 and 72 hours after randomisation) and then every 24 hours till the patient is discharged from the ICU

Exploratory endpoints

The following parameters will be measured only on UK patients at 12, 24, 48, 72 and 96 hrs after start of treatment (first dose in the poractant alfa group) or after randomisation (in the control group):

- Change from baseline in lowest and dynamic surface tensions (mN/m) from TA samples
- Change from baseline in concentrations of surfactant phospholipids (mg/ml) and proteins (ng/ml) from TA samples
- Change from baseline in inflammatory indices such as cellular and cytokine (pg/ml) inflammatory markers (e.g. IL-1, IL-6, TNF alpha, IFN gamma and lymphocyte markers) from TA and blood samples

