4.2 Safety Variables

- Adverse events (AEs).
- Laboratory parameters.
- Vital signs (blood pressures and pulse rate).

5 Sample Size

A total of 70 subjects will be randomised in the study with a ratio 3:2 (i.e. 42 subjects randomised to the poractant alfa group and 28 in the control group). Assuming subjects in the control arm being free from ventilation on average 1 week (i.e. 7 days), this sample size achieves 84% power to detect a difference of 4 days (i.e. on average 11 ventilation-free days for subjects treated with poractant alfa), assuming a standard deviation of 5.5 and a two-sided significance level (alpha) of 0.05 using a two-sample t-test.

6 Analysis Set

The definition of the analysis set is summarized below. A final agreement on the subjects to be included in or excluded from the analysis set will be reached during the review of the data

before database lock. Inclusions and exclusions from the analysis set will be fully documented in the Data Review Report.

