Listing 16.2.6.2-b	Ventilatory Derived Parameters by Timepoint (Intention-To-Treat Set)	-	
 - Display: - Subject ID - Randomized Treatment - Actual Treatment - Parameter <Unit> 
 - Number of Days Free From Invasive Ventilation - Number of Days Free From Non-invasive Ventilation - Mortality - Number of Days Alive and Ventilator-free - Alive and Free of Respiratory Failure - Alive and Out of ICU - Length of Primary ICU Stay (Days) - Length of Secondary ICU Stay (Days) - Length of Total ICU Stay (Days) - Alive and Organ Failure Free - Severity PaO₂/FiO₂ ratio - Improvement in Severity PaO₂/FiO₂ ratio - Values (display one column for Baseline, one for D21 and one for D28 results) 
Add the following Flags as relevant at D21 and/or D28 results:
 
 - Min 12H Ventil. Free - Min 12H Inv. Ventil. Free - Min 12H NInv. Ventil. Free 	Add the footnotes: 
 [1] * Flag subject with minimum 12H of ventilation free [2] ^ Flag subject with min 12H of NIV free [3]# Flag subject with minimum 12H of IV free

Listing Number	Listing Title	Template Code	Notes	Footnotes
Listing 16.2.6.3	SOFA Score (Intention-To-Treat Set)	VSL002	
 - Remove 'Analysis Period' - Display 'Assessment date [Study Day]' instead of 'Assessment date/time [study day / study day in period]' - Do not display [H] flag in Change from baseline column - Skip the last column (Change from pre-dose) - Do not display the unit in column 'Test' (no unit for SOFA score) - In Test column, display: 
 - Respiratory system Score - Nervous system Score - Cardiovascular system Score - Liver Score - Coagulation Score - Kidney Score - SOFA Score (derived) 	Add the footnotes: [1]: Baseline: Y flags baseline value [2]: Use=Y: included in the analysis

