Listing 16.2.6.4	Blood Gas Analysis (Intention-To-Treat Set)	VSL002	
 - Remove 'Analysis Period' - Display 'Assessment date/Time [Study Day]' instead of 'Assessment date/time [study day / study day in period]' - Do not display [H] flag in Change from baseline column - Skip the last column (Change from pre-dose) - In Test <Unit> column, display: 
 - pH - pCO2 (mmHg) - paO2 (mmHg) - HCO3 (mmol/L) - Lactate (mmol/L) 	Add the footnotes: [1]: Baseline: Y flags baseline value [2]: Use=Y: included in the analysis [3] Duplicated data reported twice at 2 different timepoints are reported at the first occurrence for post dose/post randomisation and at the last occurrence for pre dose/pre randomisation.

Listing Number	Listing Title	Template Code	Notes	Footnotes
Listing 16.2.6.5	Hospitalization (Intention-To-Treat Set)		Variables to be listed: - Subject ID - Randomized Treatment - Hospitalization Type - Admission Date/Time [Day] - Discharge Date/Time [Day] - Hospital Stay (days) - Hospital Transfer (Date [Day]/Destination)	Add the footnote: [1] Hospital Stay has been calculated as the difference between discharge date and admission date +1.
Listing 16.2.6.6	Tracheal Aspirate and Blood Samples (Intention-To-Treat Set)	LBL001	- Remove 'Analysis Period' - Display 'Assessment date/Time [Study Day]' instead of 'Assessment date/time [study day / study day in period]' - Do not display CSA [4] column - Add a column with LBSPEC 'Sample from' with Tracheal Aspirate and blood as value - In Test <Unit> column, display: Surfactant Function measuring surface tension (mN/m) from TA samples. - Mass spec lipid analysis (%) from TA samples. - Protein D Enzyme Linked Immunosorbent Assay (ng/mL) from TA samples. - Surfactant Protein D Enzyme Linked Immunosorbent Assay (ng/mL) from Blood samples. - Cytospin from TA samples There is no normal range for TA aspirates samples, Normal range and ABN column will remain empty.	Add the footnotes: [1] Baseline=Y flags baseline value [2] USE=Y: included in the analysis [3] H = Abnormally High Value / L = Abnormally Low Value, compared to the Normal Range. [4] No Normal range for tracheal aspirate samples [5] ND: Not Done, BLOQ: Below the lower limit of quantitation

Listing Number	Listing Title	Template Code	Notes	Footnotes

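### SAP 9.3.9 has no readmission condition, so a patient readmitted and still in ICU on Day 28 can be counted as alive and out of ICU

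*SAP*

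**What the plan says.** The endpoint is worded as a status on a given day. Protocol section 8 has "Percentage of patients alive and out of ICU" at Day 28, and SAP 4.1.2.2 has "Percentage of subjects alive and out of ICU" at Day 28.

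SAP 9.3.9 derives it from two conditions joined by AND:

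- on the Patient Status form at the Day 28 follow-up "visit, the subject is still alive";
- "Date of ICU discharge Visit < Date of" the Day 28 follow-up visit.

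Neither condition mentions readmission.

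SAP 9.3.8, on length of ICU stay, does: "In case of readmission in ICU, the duration of the primary one and the readmission will be added". Listing 16.2.6.2-b accordingly has a row beginning "Length of Secondary ICU Stay (Days", beside the primary and total stays. Listing 16.2.6.5 (Hospitalization) shows the type of hospitalisation, with a column beginning "Admission Date/Time [Day" and a matching discharge column.

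Protocol 12.3.5 planned a logistic regression for this endpoint. SAP section 12 drops it because the study closed below 70 subjects, and only the summarised percentage remains.

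**The concern.** A discharge before Day 28 is a past event, while being out of ICU on Day 28 is a present state. The two agree unless a patient goes back to ICU, and the SAP itself expects that some may. For a patient whose readmission is still open on Day 28, the rule can report recovery when the patient is in intensive care. An error from this source can only turn a failure into a success. With the regression dropped, the percentage by arm is all that will be reported for this endpoint, so the error would pass straight into the result.

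**Working it through.** **Plan's own figure.** The documents give no figure for this endpoint. The one design figure, 84% power for the primary endpoint (SAP section 5), reproduces. With 42 and 28 subjects, a difference of 4 days and SD 5.5, the noncentrality is 4 / (5.5 × √(1/42 + 1/28)) = 2.98, and a two-sided 5% t-test on 68 df has power 83.6%. Nothing below depends on it.

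**Step 1: apply the rule to constructed ICU histories.** Every patient is alive, and the follow-up visit falls on Day 28. Because 9.3.9 does not say which discharge date applies, the rule is run with the first date and with the last recorded date.

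| History | Rule, first discharge | Rule, last recorded discharge | Actual status on Day 28 |
|---|---|---|---|
| A. Discharged Day 15, not readmitted | success | success | out of ICU |
| B. Discharged Day 15, readmitted Day 22, no second discharge date | success | success | **in ICU** |
| C. Discharged Day 15, readmitted Day 22, discharged Day 35 | success | failure | **in ICU** |
| D. Discharged Day 15, readmitted Day 20, discharged Day 25 | success | success | out of ICU |
| E. Never discharged | failure | failure | in ICU |
| F. Discharged on Day 28 | failure | failure | depends on the same-day convention |

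B is wrong on both readings. C is wrong only if the first date is used. D shows that a readmission closed before Day 28 does no harm.

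**Step 2: does another section settle which date is used?** SAP 7.9.4 takes the visit date as the earliest assessment date within the visit, and the study schedule has a single ICU discharge visit. If a second discharge were entered under that visit, the earliest date would be the first discharge, and C would be misclassified too. How sites enter a second discharge is not stated. Participation ends with the Day 28 follow-up (Protocol 3.2), so a later discharge date may well not be recorded. I would therefore expect B to be the usual form of the data.

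**Step 3: size.** Arm sizes come from SAP section 5 ("A total of 70 subjects will be randomised in the study with a ratio 3:2", that is 42 and 28). If k patients are misclassified in an arm of n, the percentage is overstated by 100 × k/n points.

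| k (assumed) | n = 42 | n = 28 |
|---|---|---|
| 1 | 2.4 | 3.6 |
| 2 | 4.8 | 7.1 |
| 3 | 7.1 | 10.7 |

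The final arm sizes are not in the documents. For illustration, an assumed arm of 12 gives 100 × 1/12 = 8.3 points per patient.

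**The case against.** The best defence is that the consequence is small. This is one of the other secondary variables and is reported descriptively. The listings show first and second stays with their dates, so a careful reader could spot a misclassified patient. That stands as a limit on importance. A visible error is still uncorrected in the table, however.

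Several stronger readings are tempting, and the documents do not support them:

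- A reader might infer that 9.3.8 and 9.3.9 contradict each other. One gives a duration and the other a status. In history B, with ICU entry on Day 1 and the 28-day assignment for death or prolonged ventilation not applying, 9.3.8 gives 15 + 7 = 22 days. That total does not say where the patient was on Day 28. The exact statement is that one section has a readmission rule and the other lacks it.
- A reader might apply a readmission rate to the whole arm. An assumed 2–10% of 42 is 0.8 to 4.2 patients. That is at most an upper bound for the assumed rate, because only readmissions still open on Day 28 count, among patients already discharged once and still alive.
- A reader might infer that the whole rule errs only towards success. That holds for the readmission gap. The strict inequality works the other way in history F.
- A reader might expect the error to favour one arm. Nothing in the documents shows that readmission would differ by arm.

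**Conclusion.** The point holds as a derivation rule that gives the wrong answer for a patient type the SAP foresees. A readmission open on Day 28 with no second discharge date is scored a success on any reading. One with a later recorded discharge is scored a success if the first discharge date is used.

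The overstatement is 2.4 or 3.6 points per patient at the planned arm sizes, and larger in arms that closed below plan. How many patients are affected cannot be derived from the documents, and it may be none. No hypothesis test, power figure, primary result or key secondary result depends on this endpoint.

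**What to change.** In SAP 9.3.9, define success as alive at Day 28 and no ICU stay, primary or readmission, open on Day 28. Derive it from the ICU admission and discharge dates planned for Listing 16.2.6.5. Three details need stating:

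- ICU admissions after Day 28 are ignored. Asking merely for no later admission would wrongly fail a patient readmitted on, say, Day 30.
- How a discharge on Day 28 itself is classified. The present strict inequality makes it a failure, and any change should be deliberate.
- Whether the reference is calendar Day 28 or the date of the follow-up visit.

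The cost is a sentence or two and one programming condition, and no new data appear to be needed. The downside is small. The SAP is already final, the trial is open-label, and the documents do not make clear whether the database was locked before the SAP was finalised. If it is locked, the corrected derivation should be reported in the CSR as a deviation from the SAP, as the SAP introduction provides. Showing the percentage under both rules would let readers see whether any patient changes category.
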